11.1 Extent of Exposure

Exposure to the IP will be summarized descriptively, including the following:

- Duration of exposure [months], calculated as exposure in days/30.4375, using NSD, AI, and overall,
- Duration of exposure [years], calculated as exposure in days/365.25, using NSD, AI, and overall,
- Number of injections,

- Total cumulative number of injections,
- Number of subjects transitioned to AI,
- Number of subjects with more than 12, 15, 18, 21, ... (3-month increments) months of exposure during NSD use, during AI use, and overall,
- Number of subjects with more than 12, 15, 18, 21, ... (3-injection increments) injections using NSD, using AI, and overall,
- Total cumulative dose received [mg],
- Total subject years of exposure.

The listing of individual subject data will include all variables presented in the summary tables. The same listing will include overall compliance and the planned number of injections (see [Section 10.6](#) for derivation).

An additional listing by subject and by injection will show all injection details from the subject diary: date, start time, end time, number of syringes and whether the injection was in the abdomen (yes/no). Any issue with the injections recorded on the Device Event page of the eCRF will be included in this listing as well. Bar charts will be produced for the duration of exposure in months and the number of injections, by injection device and overall.

11.2 Adverse Events – Coding and Definitions

TEAEs are AEs which start on or after the date and time of the first administration of study treatment. TEAEs occurring until the Follow-up Visit will be summarized.

Where AE start dates and/or times are missing or partially missing, AEs will be assumed to be treatment-emergent, except if the partial start dates and/or times or the AE end date and/or time indicate that the AE started before the first administration of IP.

Table 4 TEAE Assignment in Case of Missing AE Start Date Elements

Missing elements of AE start	Rule	
Regardless of any missing information for AE start: AE end date / time < first IP start date / time		non-TEAE
Otherwise (ie, if AE end date / time \geq first IP start date / time or AE end date is missing, or AE is ongoing)		
- all		TEAE
- day and month	AE start year \geq IP start year	TEAE
	AE start year < IP start year	non-TEAE
- day	AE start month / year \geq IP start month / year	TEAE
	AE start month / year < IP start month / year	non-TEAE
- time	AE start date \geq IP start date	TEAE
	AE start date < IP start date	non-TEAE

Similarly, for subjects who transitioned to AI, where start dates and/or times of a TEAE are missing will be assumed to be on AI, except if the partial start dates and/or times or the AE end date and/or time indicate that the AE started before first dose with AI. The AI reference date/time will be used instead of the IP start date/time (see [Section 8.2.1](#)).

All reported AEs regardless of when they occurred will be listed.

COVID-19 associated AEs will be identified using the COVID-19 SMQ and will generally be included in TEAE tables identified by their standard MedDRA coding.

If for a TEAE the relationship to study treatment is missing the worst case will be assumed for summarizing analysis (ie, the relationship to study treatment will be assumed to be “Yes”). If the AE or SAE with missing relationship started before the first injection of study treatment it will be considered as “not related” (realistic case). No other imputations for missing AE information will be done.

AEs will be coded using MedDRA. There will be periodic updates of the MedDRA version. The latest licensed version will be used, and version updates will be implemented upon availability. AEs will be primarily classified by MedDRA PT. Analyses will be performed by SOC and PT. Aggregated incidences at SOC level and any TEAE will also be provided.

Subjects with multiple occurrences of the same TEAE will be counted once in the total of those experiencing this PT. Similarly, a subject with one or more PT in a SOC will be counted once in the total of those experiencing PTs in that SOC. Percentages for subject incidence rates will be based on the Safety Analysis Set.

Injection site reactions (ISRs) will be identified by CSL expert review. Prior to the PARM, a list of reported terms and PTs of AEs observed in the study will be provided to CSL as an Excel file. This Excel file will be reviewed by CSL and terms identified as ISRs will be flagged, and the flag will be imported in the ADaM for AEs. ISRs will be considered as a virtual SOC, and ISRs will be reported both under the virtual SOC “Injection Site Reactions” and under their MedDRA SOC. ISRs will be counted towards the “Any” row only once.

TEAEs will be considered clearly identified to be related to an HAE therapy other than CSL312 during the Follow-up Period, if they fulfill all the following criteria:

1. The start date of the TEAE is in the Follow-up Period and is at least 30 days after the last dose of CSL312,
2. The TEAE is an ISR with start time within 72 hours after the start of the administration of another HAE medication, defined as a medication which started in the Follow-up Period, and has the primary indication ‘Study Indication (Acute HAE Treatment or HAE Prophylaxis)’ according to the eCRF form ‘Concomitant and Prior Medications’.
3. The TEAE is considered not related to study treatment or to a device issue and did not occur with overdose of study treatment according to the eCRF form ‘Adverse Events/SAEs’.

TEAEs with partially missing date will never be considered to be clearly identified to be related to an HAE therapy other than CSL312.

The AESIs defined for this study are:

- Thromboembolic events.
- Bleeding events.
- Severe Hypersensitivity / Anaphylaxis.

Note that non-systemic thrombosis (eg, localized thrombosis associated with vascular access) is not considered an AESI.

In addition to AESIs reported by the investigators according to their judgment, the following suggestive events will be independently identified for further review with a SMQ search:

- Thromboembolic events (TEE) – SMQ “Embolic and thrombotic events (SMQ)” (narrow), consisting of:
 - Embolic and thrombotic events, arterial (SMQ),
 - Embolic and thrombotic events, venous (SMQ),
 - Embolic and thrombotic events, vessel type unspecified and mixed arterial and venous (SMQ).
- Bleeding events – SMQ “Haemorrhages (SMQ)” (narrow),
- Hypersensitivity including anaphylaxis – SMQ “Hypersensitivity (SMQ)” (broad), Anaphylactic reaction (SMQ) (broad), Anaphylactic/anaphylactoid shock conditions (SMQ) (broad). Here, broad scope includes narrow and broad search.

In the following, these will also be referred to as “AESI as identified via SMQ”.

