3.4 Planned Study Duration

The duration of the study for a **CSL312-naïve subject** is expected to be a minimum of 17 months. This estimation is based on:

- An up to 1-month Screening Period.
- An up to 2-month Run-in Period.
- A minimum of a 12-month Treatment Period.
- A 2-month Follow-up Period.

The duration of the study for a **previously treated CSL312 subject** is expected to be a minimum of 14 months in this study. This estimation is based on:

- A minimum of a 12-month Treatment Period.
- A 2-month Follow-up Period.

Per Amendment 1, the duration of treatment for an individual subject is estimated to be a minimum of 12 months. The treatment duration for each subject will be variable. In addition, the study may be stopped in a specific country either after garadacimab obtains regulatory approval or it becomes commercially available in the respective country. The Sponsor reserves the right to stop the study at any time.

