- The presence of prodromal symptoms by themselves are not considered as HAE attacks.

- Subject reported use of on-demand medication to treat the prodromal symptoms by itself will not be confirmation that an HAE attack occurred.
- Any use of on-demand medication associated with prodromal symptoms only, will be reported as concomitant medication in the CRF and not as an HAE on-demand medication.

HAE symptoms that are confirmed as HAE attacks by the Investigator or delegate will be recorded in the CRF (See Section 2.4.1) as such and will be used for the primary efficacy analysis. All HAE symptoms reported by the subject will be displayed in a by-subject listing. Note: that the assessment and outcome need to also be recorded in the subject's medical records.

Symptoms reported as AEs

The investigator or designee will evaluate the symptom data entered in the eDiary by the subject using the standardized set of requirements to determine if the symptoms reported constitute an HAE attack or not. If the investigator confirms the symptoms as an HAE attack, then the HAE attack will be reported in the CRF. If the assessment of the symptoms are not confirmed as an HAE attack, then the etiology of the symptoms must be reported and recorded as an AE.

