For subjects naïve to CSL312, there will be a Screening Period of up to 1 month followed by a Run-In Period, which may last at least 1 month and up to 2 months. CSL312-naïve subjects who meet all eligibility criteria during the Run-In Period will then enter the Treatment Period. Subjects who complete Studies CSL312_3001 and CSL312_2001 according to their respective protocols will be offered the opportunity to continue treatment by entering the CSL312_3002 Open-label Treatment Period. Subjects who reach the end of treatment or terminate the study early will have a follow-up phone call 2 months after the End of Treatment (EOT) Visit. Subjects may switch to a HAE prophylaxis medication during the Follow-up Period.

The study schematic is shown in Figure 1.

Figure 1 CSL312_3002 Study Schematic

EoT = end of treatment; HAE = hereditary angioedema; OL = open-label

^a Follow-up Visit may be conducted via telephone instead of at the study site. This visit is only applicable for subjects ending study participation following the original protocol (for subjects who consent into the Protocol Amendment 1, refer to Schedule of Assessments: Treatment Period for All Subjects Under Amendment 1).

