On-demand HAE medication will be summarized as separate block within the summaries of prior and concomitant medication (as a “virtual” ATC class “On-demand HAE Medication”). The on-demand HAE medication will also be reported in their original ATC class.

Technical Note: On-demand HAE medications prior to Run-in Period are collected in the eCRF form ‘Concomitant and Prior Medications’ with Primary Indication as ‘Study Indication Acute HAE Treatment’. On-demand HAE medications on/after start of the Run-in Period are collected in a separate eCRF form ‘On-demand Treatment’. On-demand medication during the treatment period given for pre-procedure prophylaxis instead of an HAE attack is also documented on the CM and Prior Medication form with the indication “Study Indication (Pre-Procedure/Short Term HAE Prophylaxis”.

For rollover subjects, on-demand HAE medications for attacks that occurred during the Run-in Period of the lead-in study will be imported from the final analysis datasets of the respective lead-in study. Study day will be recalculated to be relative to the reference date for CSL312_3002.

Tables and listings will be provided for ATS.

A listing of prior/concomitant medication will be provided, including the flag for prior medication taken during the run-in period. Non-pharmacological procedures will be listed.

10 Efficacy Analyses

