11.3 Analysis of Primary Safety Endpoint

All analyses described in this section are applicable for C1-INH HAE subjects only. TEAEs will be presented for the following:

- All subjects in the Safety Analysis Set (all subjects on 200 mg CSL312 once monthly, independent of the use of CSL312 200 mg AI or CSL312 200 mg NSD).
- Subjects on 200 mg CSL312 using AI.
- Subjects on 200 mg CSL312 using NSD.

TEAEs will be summarized by the number of subjects and percentage of subjects experiencing at least 1 TEAE, the number of events, as well as the event rates per injection and per subject year.

TEAE rates per injection will be calculated as follows:

$$\text{TEAE Rate per Injection} = \frac{\text{Number of TEAEs}}{\text{Number of injections}}$$

where the number of injections will be the sum of the injections that subjects received during the respective safety evaluation period with the respective device (NSD, AI, or overall) the TEAE is assigned to.

TEAE rates per subject years will be calculated as follows:

$$\text{TEAE Rate per Subject Year} = \frac{\text{Number of TEAEs}}{\text{Subject years}}$$

where subject years will be the sum of the time in years that subjects were exposed to study treatment using that device (NSD, AI, or overall) during the respective safety evaluation period.

An overview summary of TEAEs will be provided including:

- TEAE,
- SAEs,
- Deaths,
- ISRs,
- TEAEs occurring within 24 hours of start of IP administration,
- SAEs occurring within 24 hours of start of IP administration,
- Related TEAEs,
- Related SAEs,
- TEAEs leading to study discontinuation,
- TEAEs in each severity category,
- ISRs, in each severity category,
- TEAEs in each outcome category,
- SAEs in each severity category,
- SAEs in each outcome category,
- AESIs, both as reported by the investigators and as identified via SMQ (see [Section 11.4](#) for definitions).

A summary table by SOC and PT will be provided.

These two summaries will exclude all TEAEs clearly identified to be related to an HAE therapy other than CSL312 during the Follow-up Period. Both summaries will be repeated for TEAEs that can clearly be identified to be related to an HAE therapy medication other than CSL312.

To evaluate the COVID-19 impact on the primary endpoint the overview summary of TEAEs and the summary table by SOC and PT will be repeated as a sensitivity analysis excluding all COVID-19 related TEAEs (per the corresponding SMQ).

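### The rule that takes other-drug injection site reactions out of the primary TEAE tables does not read the form on which on-demand HAE drugs are recorded, and it leaves non-study garadacimab undefined

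*SAP*

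**What the plan says.** SAP Section 11.2 classes a TEAE as clearly related to an HAE therapy other than CSL312 if three criteria all hold.

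1. It starts in Follow-up, at least 30 days after the last CSL312 dose.
2. It is an ISR that starts within 72 hours after administration of another HAE medication began. That medication is "defined as a medication which started in the Follow-up Period, and has the primary indication" of acute HAE treatment or HAE prophylaxis on the 'Concomitant and Prior Medications' form.
3. It is recorded as not related to study treatment or a device issue, and did not occur with an overdose.

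SAP Section 11.3 then applies the flag to the overview and the SOC/PT table for the primary endpoint: "These two summaries will exclude all TEAEs clearly identified to be related to an HAE therapy other than CSL312 during the Follow-up Period". Both tables are repeated for the flagged events alone. The all-subject tables in Section 11.4 keep the flagged events, and the listings mark them.

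The technical note in SAP Section 9.4 says where on-demand drugs are recorded. For the time before Run-in: "On-demand HAE medications prior to Run-in Period are collected in the eCRF form" 'Concomitant and Prior Medications'. After that: "On-demand HAE medications on/after start of the Run-in Period are collected in a separate eCRF form", 'On-demand Treatment'.

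On what follows treatment, SAP Section 4 says: "Subjects may switch to a HAE prophylaxis medication during the Follow-up Period". Protocol Section 3.4 adds that "the study may be stopped in a specific country either after garadacimab obtains regulatory approval or it becomes commercially available" in that country.

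**The concern.** Criterion 2 names acute treatment as a qualifying indication, yet it searches a form that, by the SAP's own account, does not hold on-demand treatment of attacks during the study. The rule therefore cannot do half of what it sets out to do.

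An ISR after a rescue injection in Follow-up would remain in the primary overview, which has its own rows for ISRs and for ISR severity. It would also enter the numerator of the TEAE rate per injection, whose denominator is the number of CSL312 injections given with the study device. For subjects who moved to the autoinjector, SAP Table 3 runs the after-transition safety period to the Follow-up Visit, so the event would fall in the autoinjector column. The separate other-therapy summaries would be incomplete for the same reason.

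The second issue is one of definition. The heading of the rule speaks of therapies other than CSL312. The operational definition uses only the start period and the indication, and names no active substance. The protocol's List of Conventions says that CSL312 is garadacimab. Country closure may follow approval or marketing of garadacimab, and prophylaxis may be started in Follow-up with no drug excluded. A programmer working from criterion 2 alone would have no instruction for a commercial garadacimab record.

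**Working it through.** The plan gives no figure on this point, so the check is a comparison of texts followed by a literal application of the three criteria.

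**Step 1. Which on-demand records can be on the form that criterion 2 reads?**

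- Before Run-in: on the form, but these records cannot have started in Follow-up, so criterion 2 fails.
- For an attack, from the start of Run-in onward: on 'On-demand Treatment'. Section 9.4 gives no end date, so Follow-up is covered. Criterion 2 fails because it does not read that form.
- Before a procedure: "On-demand medication during the treatment period given for pre-procedure prophylaxis instead of an HAE attack is also documented on the CM and Prior Medication form". The note concerns the treatment period and uses a different indication label, so criterion 2 fails.
- For prodromal symptoms alone: Protocol Appendix 2, Section 2.4, says "Any use of on-demand medication associated with prodromal symptoms only, will be reported as concomitant medication in the CRF". Criterion 2 can be met.

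Only the last route lets the acute part of the rule take effect.

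**Step 2. Literal application of criteria 1 to 3.** Illustrative assumptions: an ISR 24 hours after the other drug, 40 days after the last study dose, judged not related, unless the row says otherwise.

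| Drug given in Follow-up | Form or reading | Flagged and removed from the primary summaries? |
|---|---|---|
| Different long-term prophylaxis | Concomitant and Prior Medications | Yes |
| On-demand drug for a confirmed attack | On-demand Treatment | No |
| On-demand drug for prodromal symptoms only | Concomitant and Prior Medications | Yes |
| Pre-procedure use, other indication label | Concomitant and Prior Medications | No |
| Commercial garadacimab; last CSL312 dose taken as last study dose | Concomitant and Prior Medications | Yes |
| The same, but ISR judged related to study treatment | Concomitant and Prior Medications | No |
| Commercial garadacimab counted as a CSL312 dose (1 day before the ISR) | Concomitant and Prior Medications | No, criterion 1 fails |

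The prophylaxis part works as intended for a different drug. The acute part misses its main target. For commercial garadacimab the result turns on two things that the SAP does not settle: whether the last CSL312 dose means study doses only, and how the investigator answers the causality question when the injection was not study treatment.

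**Step 3. Effect of a missed event on the primary rate.** In SAP Section 11.3, rate per injection = number of TEAEs / number of injections received with the device. Each missed ISR adds 1 to the numerator and 0 to the denominator.

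**Step 4. Size.** An estimate would need three quantities: the number of attacks treated in Follow-up, the share treated with an injected drug that can cause an ISR, and the ISR rate per such injection. The documents give none of them. Protocol Section 5.2.1.1 permits intravenous C1-INH and other drugs of the subject's choice, and Appendix 2 says that mild attacks may need no on-demand drug. The number of attacks also depends on how many subjects start new prophylaxis, which is not stated.

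**The case against.** Four arguments stand against the point.

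First, a missed event is kept, not lost, and that is cautious in a safety table. A TEAE is defined by timing. An ISR judged not related would not appear under related TEAEs. The category is deliberately narrow, since events with partial dates never qualify. This stands: a reader might infer that the missed reactions are attributed to CSL312 as caused by it, and the documents do not support that. They are counted as TEAEs and no more. What remains is that the rule names acute treatment and then cannot find it.

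Second, a reader might infer that the SAP classes commercial garadacimab as a therapy other than CSL312 and deletes its reactions. No passage says so. The governing words of the rule, together with the protocol's equation of CSL312 with garadacimab, point towards leaving such reactions in. Removal needs a study-dose-only reading of criterion 1 and an entry of not related. There is also a fair case for keeping a reaction to a non-study injection out of a rate whose denominator lacks that injection. The remaining fault is an ambiguity between the heading and the operational definition.

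Third, flagged events stay visible in the separate summaries, the Section 11.4 tables and the listings. That stands for events the rule catches. The separate summaries do not show the ISRs it misses.

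Fourth, the eCRF is not among the documents. Under Amendment 1 the eDiary is deactivated at End of Treatment, attacks in Follow-up are reported verbally, and concomitant medications are recorded at the call. Sites may have entered Follow-up rescue doses on either form. This limits certainty about what happened in practice, but not about what the SAP text says.

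**Conclusion.** The form mismatch holds on the SAP's own text. As specified, criterion 2 does not capture on-demand drugs given for confirmed attacks in Follow-up, and only prodrome-only use can satisfy its acute part. The two primary TEAE summaries therefore keep ISRs that the rule was written to set apart, and the other-therapy summaries omit them. The garadacimab issue is secondary: a missing clarification, not a stated misclassification.

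The effect is limited to ISRs in Follow-up, and the mismatch errs conservatively for CSL312. A reader might try to project Follow-up attacks from the exposure-response figures in Protocol Section 3.3.2 and turn them into a count of misplaced ISRs. The documents do not support that: they give neither a concentration at End of Treatment nor an ISR rate for any on-demand drug.

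The conclusion assumes that the Section 9.4 technical note describes data collection in Follow-up as well as in earlier periods. The note sets no end, but the eCRF would be needed to confirm it.

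**What to change.** Two changes to criterion 2 in SAP Section 11.2:

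1. Identify the other HAE medication from both the 'On-demand Treatment' and the 'Concomitant and Prior Medications' forms. Protocol Appendix 2, Section 2.4.1, requires the date and time of each on-demand administration, so the 72-hour window can be applied to these records.
2. Add to the definition of the other medication the words 'other than garadacimab from any source', so that the flag matches its heading. Show ISRs after non-study garadacimab on a separate line, because those injections are not in the per-injection denominator.

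Then derive the flag again and produce the two primary summaries and their other-therapy counterparts from it. Before programming, check the eCRF to see where Follow-up on-demand doses were entered.

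The cost is a few words in the SAP and a small programming change; on the SAP's description the data are already collected. The downside is that slightly more events may move out of the primary tables. All of them remain in the separate summaries, the Section 11.4 tables and the listings. The change should be made before database lock; after lock, SAP Section 3 provides for reporting it in the CSR as a deviation from the SAP.
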